1.0 Research Design

1.1 Purpose/Specific Aims

The overall purpose of this study is to evaluate the effect of nutritional supplementation with a well-characterized preparation of Concord grape polyphenol-soy protein isolate (**GP-SPI**) on the composition of the gut microbiota.

A. Objectives

Primary objective:

- To evaluate the effect of nutritional supplementation with GP-SPI on gut microbiota composition.

Secondary objectives:

- To evaluate the effect of GP-SPI on kidney and liver health/function via comprehensive metabolic panel (**CMP**).
- Collect fecal, blood, and urine samples and store for a microbiome-wide association study (**MWAS**, funded by R01 AT010242-01).
- Obtain consent to enter de-identified study results into microbiome and metabolome nationwide data sharing database.

B. Hypotheses / Research Question(s)

We hypothesize that healthy subjects eating a diet supplemented with GP-SPI will demonstrate an increase in intestinal abundance of *Akkermansia* spp. within a short time period as well as changes in other genera relevant to promotion of intestinal/metabolic health. Such changes may explain, at least in part, how poorly absorbed dietary polyphenols from fruits and vegetables improve human resilience against chronic metabolic diseases.

1.2 Research Significance (500 words or less)

The proposed study will test the *hypothesis* that oral supplementation with GP-SPI complex can alter the human microbiome in a direction that is consistent with improved health and metabolic resiliency. Epidemiological, clinical, and preclinical data indicate that polyphenol compounds derived from food, such as berries, fruits, vegetables, and herbs have beneficial health effects in humans (1). The B-type proanthocyanidin (**PAC**) class of polyphenols contained in grape berries, especially skins and seeds, have been associated with health benefits (2; 3); however, PACs are poorly absorbed and reach high concentration only in the colon (4) raising questions about mechanism(s) of action. We and others have shown that dietary PACs from grape and cranberry alter the gut microbiota in association with metabolic resilience (5; 6). PACs are also biotransformed by gut bacteria to yield microbial metabolites (**MMs**) that may contribute to health benefits (3).

Sensitive to temperature and pH, polyphenols are often labile and lose effectiveness once extracted. Studies in the [name] lab (7-11) have established methods to increase the stability of extracted dietary polyphenols through sorption to protein rich foods, such as SPI. The sorption process does not require any non-food additives. Dietary polyphenols extracted from blueberries and green tea were sorbed to SPI and this polyphenol-protein complex (dosed at 40 g/day for 17 days and delivering 2136 mg total polyphenols/day) was tested in human clinical studies (12; 13).

Biochemical properties of the GP-SPI food ingredient are well-documented (9; 10) and GP-SPI and SPI supplements have been tested extensively in mice (6; 9; 10; 14). The proposed study is a logical follow up to animal studies, which showed that compared to control mice fed a high-fat diet (HFD) supplemented with SPI alone, mice fed an isocaloric HFD supplemented with GP-SPI exhibited greater resistance to weight gain, adiposity, and glucose intolerance (6). These effects were accompanied by changes in murine gut microbiota composition, including increased abundance of the microbe *Akkermansia muciniphila*,

associated with metabolic resilience (6). Similar gut microbiota changes were observed in lean mice fed low-fat diet (LFD) supplemented with GP-SPI (14).

The proposed study will first investigate how short-term supplementation with GP-SPI may modify the gut microbial community in healthy participants while monitoring liver and kidney function/health. We will also perform a longitudinal, microbiome-wide association study (MWAS) to identify gut bacteria species/strains that are positively or negatively associated with GP-SPI supplementation. Metabolomics analysis will be performed on collected urine and blood samples to identify/quantify known and unknown metabolites. Shotgun metagenomic sequencing will be performed on fecal samples to generate high quality draft genomes for species/strain level identification. These dynamic data sets will serve as input for the MWAS to correlate increasing/decreasing levels of gut bacterial species/strains to increasing/decreasing metabolites in blood and urine. These bacteria-metabolite associations will then be used to infer cause-effect relationships that can be further tested *in vitro*. We expect that successful completion of these studies will contribute to mechanistic explanations for how dietary polyphenols such as grape PACs alter the gut microbiota and resulting MM to promote metabolic health.

1.3 Research Design and Methods

Overview

This is a pilot time course study to characterize the effect of GP-SPI on the gut (i.e. fecal) bacterial community of healthy subjects. Following screening, enrolled subjects will washout of PAC-rich foods for 5 days while also consuming SPI. Subjects will then consume GP-SPI over a 10-day supplementation period. Fecal, urine, and blood samples will be collected. Comprehensive metabolic panel (CMP) tests performed before and after the GP-SPI supplementation period will monitor liver and kidney health. Using deidentified fecal, urine, and blood samples collected from time course study a MWAS study (funded by R01 AT010242-01) will be performed.

Successful completion of this pilot study will yield data that will inform the design of a follow-up placebo-controlled intervention study, which will be described in a separate clinical protocol that will be submitted to IRB for approval.

A. Research Procedures

[figure not shown]

Figure 1. Clinical Study Design

Location

Screening and out-patient visits will take place in the Surgery Clinic in the Clinical Academic Building (CAB) or Surgery Department (MEB 5) and NJ Institute of Food Nutrition and Health (IFNH).

Recruitment

Prospective participants will be recruited through flyers posted locally on Rutgers University campuses and sent to university email lists (**Flyer** attached). Interested subjects will call in or email to receive further information about the study. A member of the study team will give a brief summary of the study. If the subject requests a screening appointment, the investigator will ask for verbal consent to proceed with a list

of questions (**Telephone Script** attached). Collecting this information at this time assists in expediting the paperwork during the visit and spares ineligible subjects the inconvenience of a futile appointment.

Eligibility Screening

At the screening visit (at IFNH), a member of the study team will explain the study in detail to the subject. Full explanation of study procedures and potential risks will be provided. The subject will have ample time to read the Consent and ask questions before signing and proceeding with screening procedures. A signed copy of Consent form (form attached) will be given to the subject.

After consent a participant ID will be assigned to subject. Demographics, medical history, height, and weight (**Demographics** and **Medical History** forms attached) will be recorded for each subject. Females will be given a urine-based pregnancy test onsite and result will be recorded. If inclusion criteria are met at this time, subject will be asked to schedule a visit at CAB with study nurses for a blood draw to perform CMP screening test. If CMP results are within normal range the subject will be enrolled and return to IFNH to receive study materials needed for participation in the study. If any CMP values are outside normal ranges subject will be advised that they do not fulfill all eligibility criteria, they will be given a copy of their CMP results, and if necessary, advised to see their primary care provider. All screened subjects will be documented on **Screening and Enrollment Log** (attached).

The final selection will be contingent upon the individuals meeting all eligibility criteria and deemed capable of complying with the study protocol.

Study Procedures

- Thirty subjects will be enrolled.
- **Food List:** Participants will maintain their usual diet except for a provided list of PAC-rich foods that they will be asked to abstain from for a 5-day wash-out period and during the 10-day intervention. The Food List is provided below. The goal is to have GP-SPI as the main/only source of PAC in the diet for the study period.
- **Wash-out and SPI (Day -5 through -1):** On day -5 (pre-baseline) before any supplementation, each subject will collect their fecal and urine sample. Each subject will then consume SPI twice a day (provided as pre-weighed packets of 20 g) during a 5-day wash-out period (days -5, -4, -3, -2, and -1). Subjects will be instructed to mix each packet of SPI in 250 mL of water or in a smoothie (recipe example below will be provided) using allowed foods as detailed in instructions and consume once in the morning before breakfast and once in the evening before dinner.
- **Day 0:** On the following day each subject will collect their baseline (day 0) stool and urine samples (Fig. 1). They will visit the CAB building to have a blood sample (2 tablespoons or 30 mL) drawn by a study nurse. Blood will be used for CMP test and prepared serum will be aliquoted and stored at -80 °C until processing for marker analysis and metabolomics. Analysis of day 0 samples should help isolate any effects due to SPI alone from subsequent samples collected during GP-SPI intervention. On day 0 subjects will drop off urine and stool samples at IFNH and collect GP-SPI packets. On Day 0 participants will also take a break from consuming SPI and will start GP-SPI supplementation on morning of Day 1.
- **GP-SPI (Day 1 – 10):** Each subject will receive twenty pre-weighed 20 g packets of GP-SPI. On day 1 subjects will be instructed to mix each packet of GP-SPI in 250 mL of water or in smoothie (recipe example will be provided, please see below) using allowed foods as detailed in instructions and consume the GP-SPI mix once in the morning before breakfast and once in the evening before dinner for 10 consecutive days (Fig. 1).

- Subjects will be provided with a personal blender for smoothie preparation (value ~ \$25) that they can keep.
- **Digital food diary:** Participants will be asked to take photos of all their food and drink (except water) including the study supplements with their personal mobile computing device (e.g. smart phone, iPad, or similar). Participants will be required to download the free mobile app WhatsApp to send photos with a brief description of the food items. Photos and food description may also be sent to an email address that will be created for this study ([contact]). The food diary must be kept over the 5-day SPI and wash-out period, day 0 (break day), the 10-day GP-SPI intervention period, and up until the final blood draw on day 11 (17 days total).
- **Stool samples:** Subjects will be provided with Omnigene®Gut OMR-200 kits (DNA genotek, Ottawa, Canada) or tubes containing 95% ethanol and/or tubes containing 50% glycerol (50% water) along with paper toilet accessories for easy self-collection of fecal samples; each participant will be instructed on use of stool collection materials. The Omnigene®Gut OMR-200 kit allows transport and storage of stabilized DNA at ambient temperature for 60 days. Fecal samples collected in 95% ethanol are stable at ambient temperature for 8 weeks (15). Subjects will collect samples on days 2, 4, 6, 8, and 10 and be asked to bring their samples to the IFNH laboratory as soon as possible, within 1-3 days of collection, for processing. Fecal samples will be aliquoted and stored at -80 °C until extraction. Extraction of fecal samples collected with the OMR-200 kit or 95% ethanol yields high quality DNA (as tested in [name] lab) suitable for 16S rRNA microbiome profiling, shotgun metagenomic sequencing, qPCR, and arrays. Collection of fecal samples in 95% ethanol has additional benefit that sample may be used for metabolomics analysis (16). Collection of fecal samples in 50% glycerol and freezing will allow culturing of gut bacteria for *in vitro* experiments.
- **Bristol stool scale form:** Subjects will be provided with the Bristol stool scale (BSS) form and asked to complete it for stool samples they collect on days -5, 0, 2, 4, 6, 8, and 10 of the study. Stool consistency has been shown to strongly correlate with gut microbiota richness and composition, enterotypes, and bacterial growth rates (17). Self-assessed stool consistency as categorized by the BSS is used in clinical studies as a proxy for colonic transit rate. The BSS classifies human feces into 7 consistency categories. The highest scores (6 - 7) correspond to loose stools and fast transit time (i.e. diarrhea), while lower scores (1 - 2) correspond to hard stools and longer colon transit time (i.e. constipation). Scores between 3 – 5 are reflective of easily passed stools (i.e. normal bowel movement) (18; 19). Each consistency category reflects differences in moisture. Decreased water is associated with longer transit time and less microbial growth due to lower nutrient mobility and enzyme activity (17). Bowel movement frequency in healthy adults (n= 124) was reported to range from 3 times per week to 3 times per day (19). Subjects that report at least one bowel movement per day will be recruited for ease of compliance with study protocol. In addition, the BSS form contains an extra column to capture information about menstruation during time of sample collections as this variable could impact metabolite or bacteria profiles .
- **Urine samples:** Subjects will be provided with sterile collection containers for collection of urine samples on days 2, 4, 6, 8, 10 and asked to keep samples in 4 °C fridge until transport to the IFNH laboratory to maintain metabolite stability (20). Subjects will be asked to bring their samples to the IFNH laboratory as soon as possible, within 2-3 days of collection, for processing. Urine samples will be aliquoted and stored at -80 °C until processing for metabolomics studies.
- **Blood sample:** On day 11 subjects will go to CAB to visit study nurses for a final blood sample draw (2 tablespoons or 30 mL). Blood will be used for CMP test and prepared serum will be aliquoted and stored at -80 °C until processing for marker analysis and metabolomics.

Table 1. Schedule of events and sample collections

Days	Screen	-5	0	2	4	6	8	10	11
Informed Consent	X								
Incl/Excl Criteria	X								
Med. History	X								
Height &Weight	X								
Clinic Visit	X		X						X
Blood Draw	X		X						X
Urine Sample		X	X	X	X	X	X	X	
Stool Sample		1	2	1	1	1	1	2	
Urine Pregnancy	X								
SPI		Twice a day for 5 days	Break						
GP-SPI				Twice a day on days 1 - 10					
Food Diary		Daily up until blood draw on day 11							

Food List

To ensure that GP-SPI ingredient is the main source of PAC consumed, participants will be given the below list of PAC-rich foods that they will be asked to abstain from during the washout and study period as well as a list of allowed foods. The food list is based on published quantification of PACs in commonly consumed food items (21; 22). In addition, participants will be provided with the following example smoothie recipe.

Smoothie Recipe:

- 1 banana (or another fruit from the allowed list of foods)
- 175 - 200 mL water or milk (add more or less liquid depending on preference; may also use milk substitutes like soy, almond, or rice milk)
- 1 - 2 tablespoons ice cream or yogurt (may also use frozen yogurt or non-dairy ice cream)
- 1 packet of GP-SPI
- 1 or more cubes of ice - *optional*
- Combine ingredients and blend

Plant Foods to abstain from: Study participants should abstain from the below list of plant foods for 5 days before (i.e. washout period), during the 10-day study intervention period, and until after the final blood draw on day 11. These foods contain high levels of naturally occurring proanthocyanidin compounds, major bioactives in GP-SPI ingredient, and will interfere with interpretation of results.

- Berry fruits (green grapes, red grapes, blueberries, cranberries, choke berries, strawberries, black berries, bilberry, black currant, aronia, hawthorn, rosehip, sea buckthorn) and all berry products (i.e. juices, preserves, jams, etc.)
- Plums
- Apples

- Apricots
- Cherries

- Sorghum
- Barley
- Pinto beans
- Red kidney beans
- Small red beans
- Black-eyed peas

- Almonds
- Hazel nuts
- Pecans
- Pistachios
- Walnuts
- Peanuts with skins

- Olives
- Olive oil
- All vinegars

- Dark chocolate
- Milk chocolate

- Red wine
- White wine
- Green tea
- Black tea

- Cinnamon
- Curry powder

Plant Foods allowed during study period: The below list of plant foods have undetectable levels of proanthocyanidin compounds and may be freely consumed. Vegetables are not a significant source of proanthocyanidins and those not listed below may also be freely consumed.

- Cantaloupe
- Medjool dates
- Grape fruit
- Orange
- Tangerine
- Honeydew
- Watermelon
- Pineapple
- Figs
- Tomato

- Coffee

- Artichoke
- Asparagus
- Broccoli

- Broccoli Raab
- Cabbage
- Carrot
- Celery
- Cucumber
- Eggplant
- Lettuce
- Onion
- Pepper
- Potato
- Radish
- Sweet potato
- Zucchini
- Beets

- Corn meal
- Tortilla chips
- Wheat
- Oats
- Rice
- Soybeans
- Navy beans
- Chick peas
- Macadamia nuts
- Pine nuts
- Brazil nuts

- White chocolate

- Basil
- Oregano
- Parsley
- Paprika
- Black pepper
- Mustard seeds
- Poppy seeds
- Garlic powder
- Ginger
- Onion powder
- Turmeric
- Cloves
- Chili powder

The following plant foods have low levels of proanthocyanidin compounds and may be consumed in moderation during the study period, meaning just 1 serving per day of any food from the list below.

- Pear (1 fruit)
- Nectarine (1 fruit)
- Cherries (10 cherries)
- Apricot (1 fruit)

- Kiwi (1 fruit)
- Avocado (1 fruit)
- Mango (1 fruit or 1 cup of sliced fruit)
- Banana (1 fruit)
- Persimmon (1 fruit)
- Pomegranate (1/4 cup kernels)

- Indian Squash (1 ounce or 28 g)
- Black beans (1 ounce or 28 g)
- Lentils (1 ounce or 28 g)

- Roasted peanuts (40 pieces = 1 ounce or 28 g)
- Peanut butter (1 tablespoon)
- Cashews (18 pieces = 1 ounce or 28 g)
- Chestnuts (8-10 kernels)

- Beer (1 can/bottle = 12 ounces)
- Apple juice (1 cup or 230 mL)
- Chocolate milk (1 cup or 230 mL)

A. Data Points

Data elements to be collected include: medical history, demographics, digital and written food diaries, adverse events, metabolomics data from blood and urine samples, microbiome data from fecal samples

B. Study Duration

It will take 2 years to complete this study. Each subject will participate for 17 days.

C. Endpoints

Primary endpoint:

- 1) Evaluate the effect of nutritional supplementation with GP-SPI on gut microbiota composition using 16S rRNA gene sequencing.

Secondary endpoints:

- 1) To evaluate the effect of GP-SPI on kidney and liver health/function (safety) via comprehensive metabolic panel (CMP).
- 2) Collect fecal, blood, and urine samples and store for a microbiome-wide association study (MWAS, funded by R01 AT010242-01).

Microbiome wide association study (MWAS)

Overview: Using the deidentified fecal, urine and blood samples from Part 1 of above-described parent study, we will perform a MWAS. Healthy humans have unique gut microbial communities; however, we will investigate whether supplementation with GP will promote elements of similarity in the gut microbiota and resulting microbial metabolites (MM), including PAC-derived MM and host-derived MM such as secondary bile acids (BA), that could be linked to healthy states and metabolic resilience. Such data may reveal common ecological or functional rules existing in microbiotas of healthy individuals as well as GP- or host-derived MM biomarkers with diagnostic potential. Below is an example of a MWAS work flow.

Shotgun Metagenomics Workflow

gDNA will be extracted from deidentified fecal samples. Libraries will be constructed followed by high-throughput sequencing on an Illumina HiSeq instrument (Genewiz). Cluster generation, template hybridization, isothermal amplification, linearization, and blocking, denaturing and hybridization of the sequencing primer will be performed according to the workflow specified by service provider. Prinseq (23) will be used to trim and de-duplicate raw reads. Reads that align to the murine/human genome (24) will be removed.

De novo non-redundant metagenomic gene-catalogue construction and gene abundance-profile calculations: High-quality paired-end reads from each sample will be used for de novo assembly with IDBA_UD (25) into contigs of at least 500 bp. Genes will be predicted using MetaGeneMark (26). A non-redundant gene catalogue of microbial genes will be constructed with CD-HIT. Quality reads will mapped onto the gene catalogue using SOAPaligner (27). Aligned results will be sampled and downsized to an appropriate number of reads per sample.

Co-abundance gene groups (CAGs): Individual genes will be binned in to co-abundance gene groups (CAGs) with a canopy-based algorithm (28). Raw CAGs will be removed in the subsequent analyses if they have fewer than 3 genes or 90% of the total canopy profile is distributed in no more than three samples. CAGs with >700 genes will be regarded as bacterial CAGs for further analyses. The principal component analyses of the bacterial CAGs based on the Bray-Curtis distance and Procrustes will be performed with QIIME (29). Abundance of genes identified per sample will be determined to follow changes in gene richness over time course of GP-SPI supplementation.

Assembly and taxonomic assignment of bacterial CAGs: De novo assembly will be performed for each of the prevalent bacterial CAGs which are share by more than 20% of the samples as previously described (30). The six criteria for high-quality draft genome assembly will be used from the Human Microbiome Project (http://www.hmpdacc.org/reference_genomes/finishing.php) and checkM (31) to assess the quality of the assemblies. We will identify phylogenetic taxonomy of CAGs and assign them to species or genus level using previously described methods (14).

Profiling the metagenomics of PAC-active enzymes: Genes encoding PAC-active enzymes will be identified using a modified HMMscan pipeline (<https://www.ebi.ac.uk/Tools/hmmer/>) and the best-hit alignment will be retained. Abundances of genes belonging to the same enzyme family will be summed together.

Functional Annotation: Metagenomic data will be metabolically profiled using HUMAnN (32). All high-quality reads will be aligned with Bowtie2 to the KEGG database 2014 (33), from which sequences of eukaryotes were excluded. Alignments will be transformed into bam format with SAMtools and entered into HUMAnN to obtain the abundance of pathways. The non-redundant gene catalogue and the open reading frames will be predicted from high-quality draft genomes with Prodigal and aligned to sequences using BLASTP.

Metabolomics Workflow

1) Sample preparation

a) Blood samples will be collected, centrifugated at 3000 g at 4 °C for 10 min, and serum supernatant will be aliquoted and stored frozen. Serum will be subjected to deproteinization as follows (34): 20 µL ascorbic acid (4 mg/mL) and taxifolin (internal standard; 0.25 µM) will be added to 380 µL of sample (final concentration of 1 mM). The samples will be combined with 1 mL hexane, homogenized and centrifuged for 10 min at 17 000 g. The aqueous phase will be recovered and added dropwise to 1200 ml acetonitrile (ACN), vortexed for 2 min and centrifuged for 10 min at 17 000 g. The supernatant will be recovered, and the pellet reconstituted with 400 µL ACN. After centrifugation, ACN supernatants will be combined, dried

and stored at - 80°C until analysis. Samples will be reconstituted with 100 µL of water and filtered before analysis.

b) Urine samples (100 µL aliquots) will be centrifuged (10,000 g for 10 min at 4 °C) to remove particulates followed by dilution with water (1:1 to 1:3 vol/vol). Samples (10 µl) will be added to 10 ml of ACN and centrifuged at 3000 g for 15 min. The supernatant will be collected, dried, reconstituted in 500 µl of ethanol (50 % v/v) containing 0.1 % ascorbic acid and (w/v) and transferred to HPLC vials for untargeted analyte detection by high resolution MS (20; 35).

To deplete common matrix interferences such as phospholipids, salts, and proteins and optimize sample preparation each sample supernatant produced in a) and b) may also be loaded to Oasis Prime HLB Cartridges (Waters). Sample preparation methods will be tested.

2) Chromatographic separation and high-resolution mass spectrometry (MS): Triplicates (i.e. technical replicates) of each serum or urine sample will be separated on a Dionex UltiMate 3000 Binary Rapid Separation UHPLC with Diode Array Detector with a reverse phase (RP) C18 column for retention of medium polar and non-polar analytes as well as a hydrophilic interaction chromatography (HILIC) column for retention of highly polar metabolites (35). Separation of samples on RP and HILIC columns prior to MS will provide more comprehensive metabolome coverage. To detect the greatest number of metabolites, gradient elution protocols will be optimized separately for serum and urine samples. Chromatographic separations will be followed by MS using a Thermo Scientific Q Exactive Plus Orbitrap high resolution mass spectrometer. The orbitrap provides high mass accuracy (1–2 p.p.m.), resolution up to 100,000 and dynamic range of 5,000. Data will be collected in both positive and negative ESI modes (mass range of 100–2,000 m/z).

Quality control (QC): Three kinds of QC samples will be implemented: 1) A standard mixture solution of PAC-derived MM and/or bile acids at a concentration of 1 mg/L; 2) A bulk QC sample made by pooling equal aliquots of each urine or serum sample; 3) Bulk urine or serum QC sample spiked with standard mix. These QC controls will help evaluate retention time stability, peak shape, detector response and mass accuracy. To avoid freeze-thaws QC controls will be prepared, aliquoted, and stored at -80 °C. QC samples will be injected 5 times at the beginning of the run to ensure system equilibration, and then once every 10 samples to monitor stability of analysis. Samples will be randomized to reduce systematic error associated with measurement variability (35).

3) Data processing and metabolite identification: XCMS Online software (<https://xcmsonline.scripps.edu>) will be used to identify and line up MS peaks/metabolites. Background noise will be filtered. A 0.2 min retention time and 0.002 Da mass tolerance window will be applied. Metabolites will be identified using online databases such as Chemspider, METLIN, (<https://metlin.scripps.edu/index.php>), Human Metabolome Database (HMDB) (<http://www.hmdb.ca/>), MZedDB (<http://maltese.dbs.aber.ac.uk:8888/hrmet/index.html>) and Kyoto Encyclopaedia of Genes and Genomes (KEGG) (<http://www.genome.jp/kegg/>). Metabolite profile and identification will be achieved by comparing mass, RT, MS/MS fragmentation patterns in secondary LC-MS/MS analysis, and/or against standard compounds for aglycones. We will look for particular signatures of metabolites that are significantly increased in blood after GP intake (humans) or PAC intake (mice). As many metabolites are likely to be conjugated to glucuronide, sulphate and methyl groups, enzymatic treatments will be applied to release the aglycone for quantification purposes. After enzymatic treatment, samples will be profiled and compared to untreated samples. After deconjugation an increase in the signal of particular aglycones (previously quantified) is expected. The relative increase in these signals coupled with the decrease/disappearance of the conjugated compound will be used to quantify the concentration of these metabolites.

4) Statistical analysis: To find the bacteria that respond to GP either positively or negatively (i.e. GP responders) we will omit those strains that are found to change with only SPI supplementation. To further understand how the GP responders affect host metabolic health as a group, we will derive a GP Responder

Index (GRI) based on the abundance and diversity [Heip evenness] of the identified bacteria (36). Data will be subject to two-way repeated measures ANOVA to decipher main effects and interactions between GP and SPI. $P < 0.05$ will be considered significant.

To detect significant differences in metabolites MetaboAnalyst 3.0 software (<http://www.metaboanalyst.ca/>) will be used. Principal components analysis (PCA) will transform original data variables into a smaller number orthogonal variables built from linear combinations to explain most of the data variance and cluster samples from each time-point or group to be analyzed. Significant difference ($p < 0.05$) will be determined within subject at different time-points, within group, and between groups. Variable importance in projection (VIP) scores will be estimated to select metabolites biomarkers from a partial least squares-discriminant analysis (PLS-DA). VIP scores are a weighted sum of PLS weights for each variable and measure the contribution of each predictor variable to the PLS-DA model. Compounds with VIP score > 4 represent metabolites with greatest change, which will be chosen for proof of identity. Before carrying out PCA and PLS-DA analyses, peak intensity will be controlled by a logarithmic transformation, and monitored by Pareto scaling. Methods for data preprocessing and statistical analysis will be optimized and additional corrections and tools will be applied as needed (37; 38).

Co-inertia analysis: To aid interpretation of the relationship between the bacterial responders and metabolomics datasets, they will be integrated using a multivariate method known as co-inertia analysis (CIA) (39). We expect to uncover bacterial species/strain level increases and decreases in GP-SPI-supplemented subjects that correlate with a concomitant increase and decrease in production of their metabolites.

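### Urine collection is not timed to the last packet, so soy-derived urinary metabolites can rise from the day 0 SPI reference to the GP-SPI days with no grape effect

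*Combined protocol and SAP*

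**What the plan says.** Section 1.3 (Study Procedures) gives SPI packets "during a 5-day wash-out period (days -5, -4, -3, -2, and -1"), with the instruction to "consume once in the morning before breakfast and once in the evening before dinner". The last SPI packet is therefore on the evening of day -1. For day 0 the plan says "On the following day each subject will collect their baseline (day 0) stool and urine samples" and "On Day 0 participants will also take a break from consuming SPI and will start GP-SPI supplementation on morning of Day 1"; Table 1 also marks day 0 as a break. The purpose of these samples is stated: "Analysis of day 0 samples should help isolate any effects due to SPI alone from subsequent samples collected during GP-SPI intervention".

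From day 1, participants "consume the GP-SPI mix once in the morning before breakfast and once in the evening before dinner for 10 consecutive days". For urine, "Subjects will be provided with sterile collection containers for collection of urine samples on days 2, 4, 6, 8, 10". All five are dosing days.

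The only urine sample with a stated relation to dosing is day -5, which precedes all supplementation. Sections 1.3 and 1.8 give no clock time, first-void rule or pre-packet rule for the others.

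In the statistical analysis item of the Metabolomics Workflow, the step that drops SPI-only responders is written for bacterial strains. Metabolites are tested between time-points at p < 0.05, and Section 6.1 compares GP-SPI with SPI for each outcome.

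**The concern.** GP-SPI is 5% grape polyphenols by Section 6.3 C, so most of each packet is still the soy carrier. If urine is given during the day, day 0 and days 2-10 differ in two ways: the grape polyphenols, and the hours since the last soy load. The planned comparison cannot separate them.

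Urine is the only metabolite matrix firmly planned across days 2-10. Blood for metabolomics is drawn on days 0 and 11 only, and metabolomics on ethanol-preserved stool is mentioned only as a possibility. The MWAS correlates changing bacteria with changing metabolites and uses the associations to propose cause and effect. A step up in soy metabolites just after day 0 would coincide with any bacterial change under GP-SPI and could produce false bacteria-metabolite links.

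**Working it through.** The documents give no figure for urine. Their one power calculation concerns *A. muciniphila* and does not bear on this point. The question is how far a purely soy-derived metabolite could differ between day 0 and days 2-10 when the grape effect is zero.

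**From the documents**
- Day 0 has no packet; the last SPI packet is on the evening of day -1 (Section 1.3, Table 1).
- Packets are taken before breakfast and before dinner on days -5 to -1 and 1 to 10 (Section 1.3).
- The daily amount is 40 g of GP-SPI at 5% polyphenols (Section 6.3 C): 40 × 0.05 = 2 g polyphenols, leaving 40 − 2 = 38 g of other material, mostly soy.

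**Assumed, not in the documents**
- Packets at 07:30 and 18:30, equal soy in each, instant absorption.
- First-order elimination with half-life h between 4 and 24 h.

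**Formula.** The level at time t is the sum over earlier packets of 2^(−(time since packet)/h). At 10:00 on day 0 the two latest packets were 15.5 h and 26.5 h earlier; at 10:00 on a dosing day they were 2.5 h and 15.5 h earlier. Earlier days add nearly the same factor to both, so

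ratio ≈ [2^(−2.5/h) + 2^(−15.5/h)] / [2^(−15.5/h) + 2^(−26.5/h)]

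- h = 4: (0.6484 + 0.0682) / (0.0682 + 0.0101) = 9.15
- h = 8: (0.8052 + 0.2611) / (0.2611 + 0.1007) = 2.95
- h = 12: (0.8655 + 0.4085) / (0.4085 + 0.2164) = 2.04
- h = 24: (0.9303 + 0.6391) / (0.6391 + 0.4652) = 1.42

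Summing over the actual packets (SPI packets for day 0, GP-SPI packets for later days) gives the ratio to day 0:

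| Half-life | Both at 10:00: day 2 / 6 / 10 | All at 07:00, before the packet: day 2 / 6 / 10 |
|---|---|---|
| 4 h | 9.14 / 9.15 / 9.15 | 0.98 / 1.00 / 1.00 |
| 8 h | 2.82 / 2.95 / 2.95 | 0.88 / 1.00 / 1.00 |
| 12 h | 1.79 / 2.04 / 2.04 | 0.75 / 1.00 / 1.00 |
| 24 h | 0.95 / 1.43 / 1.47 | 0.52 / 1.00 / 1.03 |

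The table leaves out SPI still present from before day 0. That residue adds 2^(−48/h) on day 2: 0.25 at 24 h, 0.06 at 12 h, and 0.02 or less at 8 h and below. At 24 h the day 2 ratios become 0.95 + 0.25 = 1.20 and 0.52 + 0.25 = 0.77. Days 6 and 10 hardly move (2^(−144/24) = 0.016 on day 6).

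**Serum check.** Days 0 and 11 both follow an evening packet with no packet that day. At the same clock time the ratio is 1.00 to 1.03.

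**The case against.** The strongest reply is that the break day does no harm by itself. The right-hand columns show this: if every participant gives a first-morning void before the packet, there is no false rise. A reader might infer that a no-SPI day 0 makes the reference invalid; the documents do not support that. The problem is the break day together with the missing timing rule. Such a rule might also sit in Figure 1 or in the participant instructions, which could not be seen. That limits the point to the visible text.

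A reader might also infer that soy metabolites will end up reported as grape-induced. That goes too far. The plan identifies compounds by mass spectrometry and standards, sends the highest-ranked ones for proof of identity, looks for metabolite signatures in blood (which is matched), and links metabolites to bacterial responders already screened against SPI. These steps could catch known soy compounds. None is a planned filter for urine metabolites, and the work also seeks unknown compounds, so the risk is reduced but not removed.

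Larger multiples can be produced by pairing an afternoon day 0 sample with a mid-morning dosing-day sample: 20 h against 3 h at a 4 h half-life gives 2^(17/4) = 19. Nothing in the plan implies such a pairing.

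Storage also differs. On day 0, "On day 0 subjects will drop off urine and stool samples at IFNH and collect GP-SPI packets", whereas later samples may wait 2-3 days in a home refrigerator. The plan requires 4 °C for stability, and no figure supports a storage bias, so this is only a reason to record times.

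Finally, this is a pilot, and the secondary endpoint for the MWAS is to collect and store samples. That limits the severity, but the correction costs almost nothing.

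**Conclusion.** The concern holds in this form: followed as written, the plan allows grape polyphenols to be confounded with time since the last soy load in urine. Under the assumed packet times, with both samples at 10:00, the false rise is about 9-fold at a 4 h half-life, 3-fold at 8 h and 2-fold at 12 h. At 24 h it is little, with ratios from 0.95 to 1.47. These figures show what is possible and do not estimate the bias, since the documents give neither half-lives nor clock times. The scope is urine metabolomics and the MWAS. A reader should not extend it to the 16S primary endpoint or the sample size, which do not use urine, or to serum, whose two draws are matched. It should be corrected but does not threaten the trial's main result.

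**What to change.** 1. In Section 1.3 (Day 0 and Urine samples) and Section 1.8, make urine on days 0, 2, 4, 6, 8 and 10 the first-morning void, taken before that morning's packet. Day -5 already precedes supplementation.
2. Record the collection time and the time of freezing for each sample. Packet intake is already photographed for the food diary, so the interval since the last packet can be checked.
3. In the Metabolomics Workflow, extend the SPI filter to urine metabolites: do not attribute to grape polyphenols any metabolite that also changed in the same direction from day -5 to day 0. This supplements matched timing and cannot replace it, because it misses soy metabolites already cleared by day 0.
4. Interpret day 2 cautiously. Only two GP-SPI packets precede a first-morning sample that day, so a longer-lived soy metabolite can read below day 0 even with matched timing.

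The cost is a line in the participant instructions, two recorded times and one sentence in the analysis text. The supplement schedule, visits and number of samples do not change. The downside is that first-morning urine misses the early post-dose peak of rapidly absorbed compounds.
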